6.3.2 Follow-up for toxicities

Patients whose treatment is interrupted or permanently discontinued due to an AE or clinically significant laboratory value, must be followed-up at least once a week (or more if clinically indicated) for 4 weeks, and subsequently at approximately 4-week intervals, until resolution or stabilization of the event, whichever comes first. Appropriate clinical experts should be consulted as deemed necessary. Consensus management algorithms for immune-related AEs have been developed and are available to assist investigators in assessing and managing immune-related AEs (refer to [Section 6.3.1](#)). In case of a toxicity suspected to be a cytokine release syndrome, the assessments outlined in [Section 7.2.2.5.5](#) must be performed.

All patients must be followed up for AEs and SAEs for 150 days after the last dose of PDR001 or 90 days after the last dose of MCS110 for patients who stopped PDR001 and continued MCS110 alone for more than 60 days.

6.3.3 Anticipated risks and safety concerns of the study drug

Appropriate eligibility criteria and specific DLT definitions, as well as specific dose modification and stopping rules are included in this protocol. Recommended guidelines for prophylactic or supportive treatment for expected toxicities, including management of study-drug induced immune related adverse events, are provided in [Table 6-4](#). The risk to subjects in this trial may be minimized by compliance with the eligibility criteria and study procedures as well as, close clinical monitoring. There may be unforeseen risks with MCS110 in combination with PDR001 which could be serious. Refer to preclinical toxicity and or clinical data found in the MCS110 and PDR001 Investigator's Brochure.

6.4 Concomitant medications

In general, concomitant medications and therapies deemed necessary for the supportive care (e.g. such as anti-emetics, anti-diarrhea) and safety of the patient are allowed. The administration of bisphosphonates is permitted.

The patient must be told to notify the investigational site about any new medications, herbal remedies and dietary supplements he/she takes after the start of the study treatment. All medications (other than study treatment) and significant non-drug therapies (including physical therapy, herbal/natural medications and blood transfusions) administered during the study must be listed on the Prior and Concomitant Medications or the Surgical and Medical Procedures eCRF. Prior antineoplastic therapies including medications, radiotherapy, and surgery are to be recorded on the separate Prior Antineoplastic Therapy eCRF during screening. Medication entries should be specific to trade name, dose and unit, the frequency and route of administration, the start and discontinuation date and the reason for therapy.

6.4.1 Permitted concomitant therapy requiring caution and/or action

Therapeutic treatment with hematopoietic colony-stimulating growth factors G-CSF or GM-CSF may only be initiated after the first two cycles in the dose escalation part of the study, unless the patient has already experienced a DLT. If available GM-CSF is preferred over G-CSF (Eyles 2006).

Treatment with erythroid stimulating agents may not be initiated during the first two cycles in the dose escalation part of the study, unless the patient has already experienced a DLT. If a patient is using an erythroid stimulating agents prior to enrollment (at least 2 weeks before start of study treatment), they may continue at the same dose.

Anticoagulants are permitted if the patient is already at stable doses of warfarin or taking stable doses of low molecular weight heparin for >2 weeks at time of first dose and INR should be monitored as clinically indicated per investigator's discretion. However, ongoing anticoagulant therapy should be temporarily discontinued to allow tumor biopsy according to the institutional guidelines.

Anti-hypertensives are allowed as concomitant medications; however, because transient hypotension has occurred during infusions of monoclonal antibodies, consideration should be given to withholding anti-hypertensive medications for 12 hours prior to infusion with MCS110 and PDR001.

Statins should be used with caution since CK elevations are commonly seen and transient CK elevations were noted in healthy volunteers and patients studies with MCS110.

6.4.2 Prohibited concomitant therapy

During the course of the study, patients may not receive other additional investigational drugs, agents, devices, chemotherapy, or any other therapies that may be active against cancer. Additionally, no other therapeutic monoclonal antibodies and no immunosuppressive medication may be administered while on this study.

Prophylactic treatment with hematopoietic colony-stimulating growth factor G-CSF or GM-CSF is prohibited since it may induce immune suppression and promote tumor growth (Eyles 2006).

The use of systemic steroid therapy and other immunosuppressive drugs is not allowed, with the only exclusion of steroids for the treatment infusion reaction, irAEs or replacement-dose steroids in the setting of adrenal insufficiency. Systemic corticosteroids required for the control of infusion reactions or irAEs must be tapered and be at doses \leq 10 mg/day of prednisone or equivalent before the next study drug administration. Systemic steroid therapy required during the course of the study to manage other concurrent medical conditions should be discussed with Novartis.

The use of live vaccines is not allowed through the whole duration of the study.

6.5 Patient numbering, treatment assignment or randomization

6.5.1 Patient numbering

Each patient is identified in the study by a Subject Number (Subject No.), that is assigned when the patient is first pre-screened (if applicable) or when the patient is enrolled for screening. The subject number is retained as the primary identifier for the patient throughout his/her entire participation in the trial. The Subject No. consists of the Center Number (Center No.) (as assigned by Novartis to the investigative site) with a sequential patient number suffixed to it, so that each subject is numbered uniquely across the entire database. Upon signing the informed consent form, the patient is assigned to the next sequential Subject No. available to the investigator through the Oracle Clinical RDC interface. Once assigned, the Subject No. must not be reused for any other subject and the Subject No. for that individual must not be changed, even if the patient is re-screened. If the patient fails to start treatment for any reason, the reason will be entered into the Screening Disposition page.

6.5.2 Treatment assignment or randomization

The assignment of a patient to a particular cohort will be coordinated by the sponsor. No randomization will be performed in this study.

6.6 Study drug preparation and dispensation

PDR001 (100 mg powder for solution for infusion) will be administered first as a 30 minute intravenous infusion (up to 2 hour, if clinically indicated). MCS110 (7.5ml of 20 mg/ml concentrate in vial) will be administered intravenously as an 1 hour infusion (up to 2 hour, if clinically indicated). At least 30 min break should occur between the two infusions.

Further instructions for the preparation and dispensation of MCS110 and PDR001 are described in the [\[Pharmacy Manual\]](#).

All dosages prescribed to the patient, all dose interruptions and all dose changes during the study must be recorded on the Dosage Administration Record CRF.

6.6.1 Study drug packaging and labeling

MCS110 is provided as open label bulk medication in a glass vial each containing 150 mg MCS110 as a 20 mg/ml concentrate solution for infusion.

PDR001 100 mg powder for solution for infusion will be supplied as open label bulk medication.

Medication labels will be coded, printed in the local language, and will comply with local regulatory requirements. The storage conditions for study drug will be provided on the medication label.

6.6.2 Drug supply and storage

Study treatments must be received by designated personnel at the study site, handled and stored safely and properly, and kept in a secured location to which only the investigator and designated site personnel have access. Upon receipt, the study treatment should be stored according to the

instructions specified on the drug labels and in the MCS110 and PDR001 Investigator's Brochure.

6.6.3 Study drug compliance and accountability

6.6.3.1 Study drug compliance

Study treatment will be administered to the patient by the study site staff. Compliance will be assured by administration of the study treatment under the supervision of investigator or his/her designee.

6.6.3.2 Study drug accountability

The investigator or designee must maintain an accurate record of the shipment and dispensing of study treatment in a drug accountability log. Drug accountability will be noted by the field monitor during site visits and at the completion of the study.

At study close-out, and, as appropriate during the course of the study, the investigator will return all used and unused study treatment, packaging, drug labels, and a copy of the completed drug accountability log to the Novartis monitor or to the Novartis address provided in the investigator folder at each site.

6.6.4 Disposal and destruction

The study drug supply can be destroyed at the local Novartis facility, Drug Supply group or third party, as appropriate

7 Visit schedule and assessments

7.1 Study flow and visit schedule

[Table 7-1](#) lists all of the assessments and indicates with an “X”, the visits when they are performed. All data obtained from these assessments must be supported in the patient’s source documentation. The table (“Category” column) indicates which assessments produce data to be entered into the clinical database (D) or remain in source documents only (S).

No CRF will be used as a source document.

Screening/baseline evaluations must be performed ≤ 21 days before Cycle 1 Day 1, except for baseline radiological evaluations which must be done within 28 days. Assessments performed as part of the screening evaluations and within 3 days prior to the first dose of study treatment, are not required to be repeated on the first dosing day.

Laboratory and radiological assessments performed as part of standard of care prior to signing informed consent may be used if performed within 21 days and 28 days respectively, of Cycle 1 Day 1.

During the course of the study visits, test and/or procedures should occur on schedule whenever possible. A visit window of ± 7 days is allowed. If the infusion of MCS110 and/or PDR001 is delayed, the visits assessments will be shifted accordingly. On PK collection days the windows are provided in [Section 7.2.3](#).

Radiological assessments must be performed ± 1 week of the scheduled date of the assessment.

For Japan only, patients are required to be hospitalized during Cycle 1.

Visit name	Category	Protocol Section	Screening Phase	Treatment Phase														Follow-up	Disease Progression F/U	Survival F/U	
			Screening	Cycle 1					Cycle 2		Cycle 3	Cycle 4					Subsequent cycles	EOT			Safety F/U
Day of cycle			-21 to -1	1	2	4	8	15	1	15	1	1	2	4	8	15	1				
Prior/concomitant medications, surgery and medical procedures	D	7.1.1.2 7.1.5 and 6.4	X	Continuous ¹																	
Physical examination	S	7.2.2.1	X	X			X	X	X	X	X	X					X	X			
Height	D	7.2.2.3	X																		
Weight	D	7.2.2.3	X	X					X		X	X					X	X			
Vital signs	D	7.2.2.2	X	X			X	X	X	X	X	X					X	X			
Performance status	D	7.2.2.4	X	X					X		X	X					X	X			
Hematology	D	7.2.2.5.1	X	X			X	X	X	X	X	X			X		X	X			
Chemistry	D	7.2.2.5.2	X	X			X	X	X	X	X	X			X		X	X			
Coagulation	D	7.2.2.5.6	X	Only if clinically significant														X			
Urinalysis	D	7.2.2.5.3	X	X					X		X	X					X	X			
Thyroid function	D	7.2.2.5.4	X	X					X		X	X					X	X			
Cytokines (E.g. IFN-γ; IL-6, IL-1, TNFα)	D	7.2.2.5.5		X	In case of cytokine release syndrome																
Pregnancy test	D	7.2.2.5.7	X						X		X	X					X	X	X ²		

Visit name	Category	Protocol Section	Screening Phase	Treatment Phase													Follow-up	Disease Progression F/U	Survival F/U	
			Screening	Cycle 1					Cycle 2		Cycle 3	Cycle 4					Subsequent cycles			EOT
Day of cycle			-21 to -1	1	2	4	8	15	1	15	1	1	2	4	8	15	1			
Virology	D	7.2.2.5.8	X																	
Antineoplastic therapies since discontinuation of study treatment	D	7.1.5																X	X ⁷	X ⁷
Tumor evaluation as per RECIST v1.1 and as per irRC.	D	7.2.1	X	Every 2 cycles from Cycle 3 Day 1 up to Cycle 9 Day 1 (C3D1, C5D1, C7D1, C9D1), then every 3 cycles until Cycle 18 Day 1 (C12D1, C15D1 C18D1). Assessment will be performed every 4 cycles thereafter, starting from Cycle 22 Day 1. For disease progression f/u, every 9 weeks ± 1 week until week 51 after study start, then every 12 weeks± 1 week until progression of disease per irRC, withdrawal of consent, or lost to follow-up.																
Tumor markers	D	7.2.1	X	X																
12-leads ECG	D	7.2.2.6.1	X	X								X						X		
Chest x-ray [for Japan only]	D	7.2.2.7	X				X													
Adverse events	D	8	Continuous																	
Study drug administration	D	6.1.1	i.v. every 3 weeks for MCS110 and PDR001																	
PK sampling	D	7.2.3	X	X ⁴	X ⁴	X	X ⁴	X			X	X	X ⁴	X ⁴	X	X ⁴	X ⁵			

Visit name	Category	Protocol Section	Screening Phase	Treatment Phase													Follow-up	Disease Progression F/U	Survival F/U		
			Screening	Cycle 1					Cycle 2		Cycle 3		Cycle 4							Subsequent cycles	EOT
Day of cycle			-21 to -1	1	2	4	8	15	1	15	1	1	2	4	8	15	1				
Immunogenicity (IG) sampling	D	7.2.3		X					X		X	X					X ⁵				
Survival contact	D	7.1.5																			X

¹ Concomitant medications are only collected until 30 day of follow-up or the start of antineoplastic therapy, whichever comes first.
 
² Urine pregnancy test should be performed every month during and at the end of 150 days safety follow-up (90 days in case patient is only taking MCS110 alone, for more than 60 days).
 
⁴ Day 2, 4, 15 sampling times are only applicable to the Phase Ib part,
 
⁵ Cycles 5 and 6 only,
 
⁶ Only on C5D1
 
⁷ In reference to Section 7.1.5, the follow-up for safety, disease progression and survival will not be performed for patients who transfer to another clinical study to continue provision of study treatment or an alternative treatment option. For all other patients, the safety evaluation period will be completed but the disease-progression and survival follow up will not be performed.
																					

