6.1.1 Dosing regimen

Table 6-1 Dose and treatment schedule

Study treatments	Pharmaceutical form and route of administration	Dose	Frequency and/or Regimen
MCS110	Liquid concentrate in vial i.v. infusion	3 mg/kg (starting dose)	Every 3 weeks
PDR001	Powder for solution for infusion	100 mg (starting dose)	Every 3 weeks

MCS110 and PDR001 will be administered once every 3 weeks via i.v. infusions over 1 hour and 30 minutes, respectively. The drugs will be administered separately with at least a 30 min break between the two antibodies. Infusions of each antibody can be extended to up to 2 hours if clinically indicated.

Both study drugs may be infused using the same i.v. access site. The same administration sequence must be followed for all patients, i.e. PDR001 should be infused first. If an infusion reaction occurs after administration of PDR001, the subsequent MCS110 infusion must be delayed until it is safe for the patient to receive MCS110 based on the clinical discretion of the investigator. The delay between PDR001 and MCS110 infusions can be up to 4 hours if clinically indicated.

A scheduled dose of ongoing study drugs may be delayed by up to 7 days to recover from previous AEs or a missed visit (see [Section 6.3.2](#)). If a scheduled dose of ongoing study drugs is delayed longer than 7 days due to an unresolved AE, the administration should be skipped and treatment resumed at a lower dose level (if meeting criteria for DLT) at the next scheduled dose. The assessment schedule will be shifted accordingly. Dose delays refer to all ongoing study drugs: for combination treatment both MCS110 and PDR001 and for single agent treatment MCS110 or PDR001. Dose modifications should follow [Section 6.3.1](#) and [Section 6.3.2](#).

The dose for MCS110 study drug will be calculated from the individual subjects' body weight as measured at the screening visit and subsequent visits prior to the administration.

After Phase Ib part, if emerging PK, PD, and safety data indicate that a flat dosing strategy of MCS110 is appropriate, then a flat dosing strategy may be implemented in the Phase II part of the study. The PK data obtained during Phase Ib part of this study will be combined with PK data from the other MCS110 clinical studies to assess the flat dosing vs. body-weight based dosing, and a flat dose may be identified for the Phase II part of this study.

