6.2.3 Guidelines for dose escalation and determination of MTD or RP2D

The maximum tolerated dose (MTD) is defined as the highest combination drug that is unlikely (< 25% posterior probability) to cause DLT in 33% or more of the treated patients in the **first two cycles (42 days)** of treatment.

The applied adaptive Bayesian methodology provides an estimate of the combinations of MCS110 and PDR001 not exceeding the MTD. Typically the MTD is a tested combination with maximum probability of targeted toxicity (DLT rate between 16% and < 33%). The use of the EWOC principle limits the risk that a potential next dose will exceed the MTD (Section 10.4.2). Adverse events and laboratory abnormalities considered to be DLTs are defined in Table 6-3.

For the purposes of dose escalation decisions, each cohort will consist of 3 to 6 newly enrolled patients who will be treated at the specified dose level. The first cohort will be treated with the starting doses of 3 mg/kg MCS110 Q3W and 100 mg PDR001 Q3W.

Patients must complete a minimum of two cycles of treatment with the minimum safety evaluation and drug exposure or have had a DLT within the first two cycles of treatment to be considered evaluable for dose escalation decisions ([Section 10.1.4](#)). Dose escalation decisions will occur when the cohort of patients has met these criteria. If only 2 of the 3 patients in a cohort are evaluable and neither subject has experienced a treatment-related toxicity > CTCAE Grade 1, dose escalation decisions may be considered.

Dose escalation decisions will be made by Investigators and Novartis study personnel. Decisions will be based on a synthesis of all relevant data available from all dose levels evaluated in the ongoing study including safety information, DLTs, all CTCAE Grade ≥ 2 toxicity data during Cycle 1 and 2, PK, and PD data from evaluable patients. The recommended dose for the next cohort of subjects will be guided by the BLRM with EWOC principle evaluating the probability of DLT ([Section 10.4.2](#))

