7.1.2 Treatment period

A treatment cycle is defined as 21 days for the purposes of scheduling procedures and evaluations. Please refer to [Table 7-1](#) for details of the timing of required assessments and [Section 7.1](#) for visit windows.

Patients will be treated until they experience unacceptable toxicity, progressive disease per irRC and/or treatment is discontinued at the discretion of the investigator or the patient, as described in [Section 7.1.3](#) and [Section 4.3](#).

Patients should not discontinue treatment based on progressive disease per RECIST v1.1.

Accumulating evidence indicates that objective responses to immunotherapy follows delayed kinetics of weeks or months, and can be preceded by initial apparent radiological progression or appearance of new lesions or some enlarging lesions while other target lesions are regressing (“mixed response”) ([Wolchok 2009](#)). It is therefore reasonable to allow for these possibilities and continue to treat the patient until progression is confirmed and found to be advancing at the next imaging assessment as per irRC. An outline of the irRC is provided in [Appendix 2](#).

These considerations should be balanced by clinical judgment as to whether the patient is clinically deteriorating and unlikely to receive any benefit from continued treatment.

Such deterioration will be assessed to have occurred after a clinical event that, in the Investigator's opinion, is attributable to disease progression, is unlikely to reverse with continued study treatment and therefore indicates that the patient is not benefiting from study treatment and cannot be managed by the addition of supportive care.

The decision to continue or stop treatment should be discussed with the Novartis Medical Responsible and will be documented in the study files.

The following criteria should be considered for treatment continuation decision making:

- Patients with partial response or stable disease as well as patients with unconfirmed progressive disease (per irRC) should continue to receive study treatment until the next cycle.

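### The 7-day visit window lets the C2D15 safety laboratory check fall on C3D1, leaving half of the 42-day DLT period without a scheduled test, and Section 7.1 does not say whether its early side covers infusion visits

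*Protocol*

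**What the plan says.** **Visit window.** Protocol Section 7.1 states, for visits in general, "test and/or procedures should occur on schedule whenever possible. A visit window of" plus or minus 7 days. It adds two qualifications. If an infusion "is delayed, the visits assessments will be shifted accordingly". And "On PK collection days the windows are provided in" Section 7.2.3.

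**Dosing.** Section 6.1.1 says "MCS110 and PDR001 will be administered once every 3 weeks via i.v. infusions". The only tolerance it gives is on the late side: "A scheduled dose of ongoing study drugs may be delayed by up to 7 days to recover from previous AEs or a missed visit". The study drug row of Table 7-1 reads "i.v. every 3 weeks for MCS110 and PDR001", cites Section 6.1.1 and has no window of its own.

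**Cycle length and DLT period.** Under Section 7.1.2, "A treatment cycle is defined as 21 days for the purposes of scheduling procedures and evaluations". Sections 6.2.3 and 6.2.4 set the DLT period at two cycles, or 42 days.

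**Safety laboratory schedule.** Table 7-1 places hematology and chemistry at C1D1, C1D8, C1D15, C2D1, C2D15, C3D1, C4D1 and C4D8, and on Day 1 of later cycles.

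**PK days.** Tables 7-6 and 7-7 give plus or minus 8 hours for C1D8 and C4D8 in both parts. Table 7-6 gives the same for Day 15 of Cycles 1 and 4 in Phase Ib. For Day 1 of Cycles 2 to 6 they say only that the sample is taken before the dose. C2D15 is in neither table.

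**Evaluability.** Section 6.2.3: "Patients must complete a minimum of two cycles of treatment with the minimum safety evaluation and drug exposure", unless they have had a DLT. Section 10.1.4 adds at least 42 days of observation and a joint judgement by sponsor and investigators that the safety data suffice. SAP Table 5-3 removes from the dose-determining set DLT-free patients who did not complete the required Cycle 1 and 2 safety evaluations.

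**The concern.** A window should be narrower than the distance to the next scheduled visit; otherwise two visits can become one without a deviation. At C2D15 the window equals that distance. The visit is the only planned look at blood counts and chemistry inside the second DLT cycle, so merging it with C3D1 removes the mid-cycle look altogether. A laboratory DLT without symptoms that arises and resolves between C2D1 and C3D1 would not be seen. The error has one direction: DLTs are undercounted, and the dose-escalation model then reads the dose as safer than the patients' course would show.

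The second issue is one of wording. A symmetric window is stated for visits, infusions take place at Day 1 visits, and the dosing section speaks only of delays. Two sites could read these sections differently, and neither reading is ruled out in so many words.

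**Working it through.** **Inputs.** Cycle length 21 days (Section 7.1.2); window plus or minus 7 days (Section 7.1); visit days (Table 7-1); PK windows (Tables 7-6 and 7-7).

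**The plan's own figure.** Two cycles: 2 × 21 = 42 days, as in Section 6.2.3.

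**Study days.** Study day = (cycle − 1) × 21 + day of cycle.

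| From | To | Study days | Gap |
|---|---|---|---|
| C1D1 | C1D8 | 1 to 8 | 7 |
| C1D8 | C1D15 | 8 to 15 | 7 |
| C1D15 | C2D1 | 15 to 22 | 7 |
| C2D1 | C2D15 | 22 to 36 | 14 |
| C2D15 | C3D1 | 36 to 43 | 7 |
| C3D1 | C4D1 | 43 to 64 | 21 |
| C4D1 | C4D8 | 64 to 71 | 7 |
| C4D8 | C5D1 | 71 to 85 | 14 |

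The window equals the gap in 5 of 8 rows. In Phase Ib, C1D8 and C1D15 are PK days with 8-hour windows. In the DLT period that leaves C2D15 as the one mid-cycle check with the full 7 days.

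**C2D15 window.** 36 − 7 = 29; 36 + 7 = 43. C3D1 is (3 − 1) × 21 + 1 = 43. The last permitted day for C2D15 is C3D1.

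**Effect.** With C2D1 and C3D1 on schedule, the planned Cycle 2 test intervals are 14 days (22 to 36) and 7 days (36 to 43). Merged, there is a single interval of 43 − 22 = 21 days, and 21/42 = 50% of the DLT period.

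**Would the evaluability rules catch it?** SAP Table 5-3 acts on evaluations not completed. A C2D15 assessment done on day 43 is completed and in window, so this criterion does not exclude the patient. The judgement in Section 10.1.4 could, but nothing directs it to the spacing of tests.

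**Infusion visits, passages side by side.** Section 7.1 has an early and a late side, does not exclude infusion visits, and mentions only a delayed infusion. Section 6.1.1 has a 3-week interval and a late side only. Section 7.2.3 gives an order on Day 1 (sample, then infusion) and no day tolerance. No section states how the three combine.

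**Would dose intensity show an early infusion?** SAP Section 2.4.1 ends exposure 20 days after the last dose and counts scheduled doses as exposure days divided by 21, rounded up. Suppose full doses on days 1, 22 and 36. Exposure is 36 + 20 = 56 days, 56/21 = 2.67, so 3 doses are scheduled. Three were given, so relative dose intensity is 100%. On schedule (days 1, 22, 43) it is 63 days, 63/21 = 3, again 100%. The summary does not separate the two.

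**The case against.** **Infusions 14 days apart.** A reader might infer that the window allows infusions 21 − 7 = 14 days apart, a dose rate of 21/14 = 150% of plan for that cycle. The documents do not support this as a permission. Section 6.1.1 and the dosing row of Table 7-1 fix dosing at every 3 weeks, and Section 7.1 provides only for delayed infusions. Day 1 of Cycles 1 to 6 is a PK day deferred to Section 7.2.3, whose lack of a day tolerance is silence, not consent. What stands is that the sections do not say how they fit together.

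**All safety visits can collapse.** A reader might also infer this from the 7-day width. It is not so: three of the eight gaps are 14 or 21 days, and the Phase Ib Cycle 1 mid-cycle checks fall under the PK windows.

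**Existing safeguards.** Section 7.1 asks for visits on time where possible. Section 10.1.4 requires joint judgement on the safety data, and Section 8.5 has each patient's course described at the escalation teleconference. These make a merge less likely to pass unnoticed. They do not make it a deviation.

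**Fewer events at stake than the panel suggests.** Table 6-3 exempts lymphopenia and leukopenia, Grade 4 neutropenia of up to 5 days without fever or symptoms, Grade 3 thrombocytopenia without significant bleeding, Grade 3 CK elevation without muscle damage, and Grade 3 isolated AST elevation. This stands. The exposure is mainly to ALT, to bilirubin with transaminases, and to Grade 4 events that are not exempt.

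**Timing.** The Amendment 05 study status reports enrollment closed, 60 escalation patients treated, and the six still on treatment in Phase II only. New wording cannot change DLT data already collected. The SAP also already lists all doses and all laboratory data, so the inputs exist. What is missing is an output that picks out the patients concerned.

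**Conclusion.** The concern holds for C2D15. A site following Section 7.1 exactly can leave a 21-day interval, half of the 42-day DLT period, without a scheduled hematology or chemistry test, and the patient can still enter the dose-determining set as DLT-free. This assumes that C2D1 and C3D1 are on schedule, that C2D15 is done on the last day of its window, and that no unscheduled test is taken in between. The documents do not say how often this happened; among the 60 escalation patients the number could be anywhere from 0 to 60. Symptomatic DLTs would still be reported as adverse events.

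For infusions the finding is an ambiguity only: Sections 7.1, 6.1.1 and 7.2.3 do not settle whether the early side of the window applies, and early infusion is not expressly permitted. No sample size or operating characteristic in the plan depends on either part.

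**What to change.** 1. In Section 7.1, give the C2D15 safety assessment a window that does not reach C3D1.
2. Reconcile Sections 7.1, 6.1.1 and 7.2.3 so that they state whether the visit window applies to infusion visits. No dosing interval is proposed here.
3. Add to the SAP a listing of Phase Ib patients with no hematology or chemistry result dated between C2D1 and C3D1, by dose level and with DLT status, and a listing of any infusion given earlier than scheduled. Both can be built from data the SAP already lists.

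The cost is slightly less scheduling freedom for sites, some protocol wording and a small amount of programming. With escalation complete, items 1 and 2 tidy the text, and item 3 is what can still show whether the gap touched the DLT evidence behind the recommended dose. If the Phase Ib listing is empty, the point closes for the DLT data.
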